8.5. Efficacy Variables

The efficacy will be assessed by using various psychometric scales. Every scale will be performed by experienced and trained raters (certified in PANSS scale) according to planned schedule of assessments.

8.5.1. Positive and Negative Syndrome Scale

The PANSS is a 30-item scale used to measure symptoms of schizophrenia. The scale has 7 positive symptom items, 7 negative symptom items, and 16 general psychopathology symptom items. Each item is scored on a 7-point scale by the clinical rater based on a clinical interview with the patient.

Positive and Negative Syndrome Scale will be performed at the time points detailed in the Schedule of Assessments (Table 1) and as detailed below:

The efficacy assessment (PANSS) will be performed once at Screening (Day -10 to -2); once at Baseline (Day -1); on Days 1, 7, 14, 21 and 28 when start of ratings is to be within 5 minutes before or after 2h post-dose (it will be performed before any other scale).

8.5.2. Clinical Global Impression Scale - Severity

The Clinical Global Impression (CGI) Scale is a standardized assessment tool that the Investigator can use to rate the severity of illness, change over time, and efficacy of medication, taking into account the patient's clinical condition and the severity of side effects. The CGI Scale consists of 3 global subscales formatted for use with the Global Scoring Sheet. The first subscale, Severity of Illness, assesses the Investigator's impression of the patient's current illness state; it is often used both before and after treatment. Scores on the Severity of Illness subscale range from 1 = not ill at all to 7 = among the most extremely ill.

Clinical Global Impression Scale - Severity will be performed at the time points detailed in the Schedule of Assessments (Table 1) and as detailed below:

The efficacy assessment (CGI-S) will be performed once at Screening (Days -10 to 2), once at baseline (Day -1); on Days 7, 14, 21 and 28 when start of ratings is to be within 5 minutes before or after 2h post-dose (after PANSS).

8.5.3. Clinical Global Impression Scale - Improvement

Clinical Global Impression Scale - Improvement is a 7 points scale that requires the clinician to assess how much the patient's illness has improved or worsened relative to a baseline state at the beginning of the intervention. CGI-I will be performed at the time points detailed in the Schedule of Assessments (Table 1) and as detailed below:

The efficacy assessment (CGI-I) will be performed on Days 7, 14, 21 and 28 when start of ratings is to be within 5 minutes before or after 2h post-dose (after PANSS and CGI-S)

8.5.4. Brief Assessment of Cognition in Schizophrenia

The Brief Assessment of Cognition in Schizophrenia (BACS) is specifically designed to measure treatment-related improvements in cognition and includes alternate forms. BACS is a reliable and sensitive measure of cognitive function in schizophrenia. The BACS is a cognition assessment battery that assesses 6 domains of cognitive function found to be consistently impaired in schizophrenia: verbal memory, working memory, motor speed, attention, executive functions, and verbal fluency. Brief Assessment of Cognition in Schizophrenia will be performed at the time points detailed in the Schedule of Assessments (Table 1) and as detailed below:

The BACS assessment will be performed at Baseline (Day -1) and on Days 14 and 28 when start of ratings is to be within 5 minutes before or after 2h post-dose (after PANSS, CGI-S and CGI-I)..

8.6. Total Amount of Blood

The maximum volume of blood planned for collection from each subject over the course of the entire study (from the Screening Visit to the final Follow-up Visit, but not including repeat or additional tests ordered by the Investigator) will not exceed 500 ml and presents no undue risk to the subjects.

8.7. Hospitalization

Patients are to be hospitalized after the screening qualification for washout period of up to 7 days (if necessary) before the start of the 28-day Treatment Period. Patients are to be hospitalized during the treatment period (Day 1 to Day 28). On Day 29 patients may be discharged from the clinical centre based on local standards of care if the patient is in stable condition under the regular medication(s).

9. STUDY SCHEDULE

9.1. Screening

Before providing the potential study patient with the information leaflet and informed consent form, the physician responsible for the enrollment provides them detailed information on:

- The purpose of the study,
- Any potential risk and inconveniences associated with the study, among others the number of visits and all study procedures that are to be performed,
- Patient's responsibilities (restrictions, sampling schedule etc.),
- Right to refuse to participate or withdraw from the study at any time,
- Confidentiality of patient's medical information,
- Person to contact for further information regarding the study and whom to contact in case of any side effects occur,
- Expected duration of the patient's participation in the study,
- Entities granted direct access to the patient's original medical records for verification of clinical study procedures.

The potential patient is to be given enough time to make a fully conscious and informed decision to participate in the study.

After obtaining the written Informed Consent Form signed and dated by the patient Screening procedures as detailed in the Schedule of Assessments (Table 1) are to be performed. For description of these procedures see Sections 8.3.2 - 8.3.9 and for all of the inclusion/exclusion criteria patients must meet see Sections 5.2 and 5.3.

Patients will undergo screening assessments from Day -10 to Day - 8 in multiple settings (i.e. emergency departments, outpatient clinics etc.). Patients that fulfil all the inclusion and none of the exclusion criteria will immediately be admitted to the Clinical Unit and enter Medication Washout Period of up to 7 days (Day -7 to Day -1) before treatment phase, if needed. The duration of Medication Washout Period may be shorter or omitted for non-medicated patients.

Approximately 165 patients who meet all of the inclusion and none of the exclusion criteria are to be enrolled into the study. Patients identification numbers (or subject identifier) are to be given to each patient during the Screening.

9.2. Baseline (Day -1)

Visit on Day -1 is to performed to confirm inclusion/exclusion criteria and collect baseline values for further assessments.

Patients identification is to be followed by alcohol test, urine drugs screen test and urine pregnancy test (for women). Vital signs measurements (respiratory rate, body temperature, 3-positional blood pressure and pulse) are to be performed, followed by 12-lead ECG. Afterwards blood and urine samples for clinical laboratory assessments are to be collected. Baseline assessment of scales is to be performed and the scales are to be performed in order as follows: PANSS, CGI-S, BACS, ESRS, C-SSRS. Afterwards physical, neurological, ophthalmological and dermatological examination are to be performed.

After all the procedures Investigator is to confirm that the inclusion/ exclusion are met. If a patient status after screening changes at Baseline (Day -1) such that the study patient no longer meets all eligibility criteria, then the patient should be excluded from participation in the study (such patient is to be considered as screen failure). It should be remembered that all baseline procedures must be performed on Day -1, but final patient qualification should be made when all results are available, before randomization on Day 0.

Requests for AEs and information about the concomitant medications if any, are to be performed by the Investigator to each patient during the study as well as patient is to be asked to report spontaneously all symptoms and complaint.

9.3. Day 0

On Day 0, the Investigator is to performed the final patient qualification to the study based on all baseline results – this is the case, when not all baseline results (especially laboratory values) are to be available on Day -1.

For a patient meeting all of the inclusion and none of the exclusion criteria the randomization procedure is to be performed.

9.4. Day 1

On Day 1, patient is to receive the first dose of IMP. Before administration (\leq 1h before IMP administration) vital signs measurements are to performed (respiratory rate, body temperature, 3-positional blood pressure and pulse). Afterwards blood and urine samples for clinical laboratory assessments, and blood sample for pre-dose PK time point (extensive and sparse group) are to be collected (\leq 1h before IMP administration). With the first PK sampling cannula might be inserted

into a vein shortly prior to the event. If there is cannula occlusion, samples may be obtained via direct venepuncture. IMP is to be administered with hand and mouth check afterwards to ensure the patient have swallowed all capsules. Serial time-points after IMP administration for PK analysis (extensive and sparse group) are to be collected in scheduled time-points (see Section 8.4.1). Within 5 minutes before or after 1h 45 minutes after IMP administration vital signs measurements are to be performed (respiratory rate, body temperature, 3-positional blood pressure and pulse). Start of ratings is to be within 5 minutes before or after 2h post-dose but after PK blood collection 2h timepoint and the scales are to be performed in order as follows: PANSS, ESRS. Within 5 minutes before or after 9h post-dose vital signs measurements are to be performed (respiratory rate, body temperature, 3-positional blood pressure and pulse).

Requests for AEs and information about the concomitant medications if any, are to be performed by the Investigator to each patient during the study as well as subject is to be asked to report spontaneously all symptoms and complaints.

Patient is to fast from supper on Day -1 (fasting at least 10 hours prior to dosing) with continued fasting for 2 hours post-dose. Water and other fluids are to be restricted one hour before and one hour after dosing (excluding amount of water allowed for IMP administration).

9.5. Days 2 to 6

On Days 2-6, patient is to receive the consecutive doses of IMP. Before administration (≤ 1h before IMP administration) vital signs measurements are to performed (respiratory rate, body temperature, 3-positional blood pressure and pulse). Afterwards blood sample for pre-dose PK time point (only extensive group) are to be collected (≤ 1h before IMP administration). IMP is to be administered with hand and mouth check afterwards to ensure the patient have swallowed all capsules. Within 5 minutes before or after 1h 45 minutes after IMP administration vital signs measurements are to be performed (respiratory rate, body temperature, 3-positional blood pressure and pulse). PK blood sample are to be collected 2h post-dose for extensive group only. Within 5 minutes before or after 9h post-dose vital signs measurements are to be performed (respiratory rate, body temperature, 3-positional blood pressure and pulse).

Patient is to fast from supper on day before (fasting at least 10 hours prior to dosing) with continued fasting for 2 hours post-dose. Water and other fluids are to be restricted one hour before and one hour after dosing (excluding amount of water allowed for IMP administration).

9.6. Day 7

On Day7, patient is to receive the consecutive dose of IMP. Before administration (≤ 1h before IMP administration). Vital signs measurements (respiratory rate, body temperature, 3-positional blood pressure and pulse) are to be performed, followed by 12-lead ECG. Afterwards blood and urine samples for clinical laboratory assessments, and blood sample for pre-dose PK time point (extensive and sparse group) are to be collected (\leq 1h before IMP administration). With the first PK sampling cannula might to be inserted into a vein shortly prior to the event. If there is cannula occlusion, samples may be obtained via direct venepuncture. IMP is to be administered with hand and mouth check afterwards to ensure the patient have swallowed all capsules. Serial time-points after IMP administration for PK analysis (extensive group) are to be collected in scheduled timepoints (see Section 8.4.1). Within 5 minutes before or after 1h 45 minutes after IMP administration vital signs measurements are to be performed (respiratory rate, body temperature, 3-positional blood pressure and pulse). Start of ratings is to be within 5 minutes before or after 2h post-dose but after PK blood collection 2h timepoint (extensive and sparse group) and the scales are to be performed in order as follows: PANSS, CGI-S, CGI-I, ESRS. Not earlier than 5h postdose neurological examination is to be performed. Within 5 minutes before or after 9h post-dose vital signs measurements are to be performed (respiratory rate, body temperature, 3-positional blood pressure and pulse).

Requests for AEs and information about the concomitant medications if any, are to be performed by the Investigator to each patient during the study as well as subject is to be asked to report spontaneously all symptoms and complaints.

Patient is to fast from supper on day before (fasting at least 10 hours prior to dosing) with continued fasting for 2 hours post-dose. Water and other fluids are to be restricted one hour before and one hour after dosing (excluding amount of water allowed for IMP administration).

9.7. Days 8 to 13

On Days 8-13, patient is to receive the consecutive doses of IMP.

Patient is to fast from supper on day before (fasting at least 10 hours prior to dosing) with continued fasting for 2 hours post-dose but starting from 0.5h after IMP administration consumption of low calorie snack i.e. plain rice cakes is allowed till breakfast. Water and other fluids are to be restricted one hour before and one hour after dosing (excluding amount of water allowed for IMP administration).

9.8. Day 14

On Day 14, patient is to receive the consecutive dose of IMP. Before administration (≤ 1h before IMP administration) vital signs measurements (respiratory rate, body temperature, 3-positional blood pressure and pulse) are to be performed, followed by 12-lead ECG. Afterwards blood and urine samples for clinical laboratory assessments are to be collected (≤ 1h before IMP administration). IMP is to be administered with hand and mouth check afterwards to ensure the patient have swallowed all capsules. Within 5 minutes before or after 1h 45 minutes after IMP administration vital signs measurements are to be performed (respiratory rate, body temperature, 3-positional blood pressure and pulse). Start of ratings is to be within 5 minutes before or after 2h post-dose and the scales are to be performed in order as follows: PANSS, CG-S, CGI-I, BACS, ESRS, C-SSRS. Not earlier than 5h post-dose neurological examination is to be performed. Within 5 minutes before or after 9h post-dose vital signs measurements are to be performed (respiratory rate, body temperature, 3-positional blood pressure and pulse).

Requests for AEs and information about the concomitant medications if any, are to be performed by the Investigator to each patient during the study as well as subject is to be asked to report spontaneously all symptoms and complaints.

Patient is to fast from supper on day before (fasting at least 10 hours prior to dosing) with continued fasting for 2 hours post-dose but starting from 0.5h after IMP administration consumption of low calorie snack i.e. plain rice cakes is allowed till breakfast. Water and other fluids are to be restricted one hour before and one hour after dosing (excluding amount of water allowed for IMP administration).

9.9. Days 15 to 20

On Days 15-20, patient is to receive the consecutive doses of IMP.

Patient is to fast from supper on day before (fasting at least 10 hours prior to dosing) with continued fasting for 2 hours post-dose but starting from 0.5h after IMP administration consumption of low calorie snack i.e. plain rice cakes is allowed till breakfast. Water and other fluids are to be restricted one hour before and one hour after dosing (excluding amount of water allowed for IMP administration).

9.10. Day 21

On Day 21, patient is to receive the consecutive dose of IMP. Before administration (≤ 1h before IMP administration) vital signs measurements (respiratory rate, body temperature, 3-positional blood pressure and pulse) are to be performed, followed by 12-lead ECG. Afterwards blood and urine samples for clinical laboratory assessments are to be collected (≤ 1h before IMP administration). IMP is to be administered with hand and mouth check afterwards to ensure the patient have swallowed all capsules. Within 5 minutes before or after 1h 45 minutes after IMP administration vital signs measurements are to be performed (respiratory rate, body temperature, 3-positional blood pressure and pulse). Start of ratings is to be within 5 minutes before or after 2h post-dose and the scales are to be performed in order as follows: PANSS, CGI-S, CGI-I, ESRS. Not earlier than 5h post-dose neurological examination is to be performed. Within 5 minutes before or after 9h post-dose vital signs measurements are to be performed (respiratory rate, body temperature, 3-positional blood pressure pulse).

Requests for AEs and information about the concomitant medications if any, are to be performed by the Investigator to each patient during the study as well as subject is to be asked to report spontaneously all symptoms and complaints.

Patient is to fast from supper on day before (fasting at least 10 hours prior to dosing) with continued fasting for 2 hours post-dose but starting from 0.5h after IMP administration consumption of low calorie snack i.e. plain rice cakes is allowed till breakfast. Water and other fluids are to be restricted one hour before and one hour after dosing (excluding amount of water allowed for IMP administration).

9.11. Days 22 to 27

On Days 22-27, patient is to receive the consecutive doses of IMP.

Patient is to fast from supper on day before (fasting at least 10 hours prior to dosing) with continued fasting for 2 hours post-dose but starting from 0.5h after IMP administration consumption of low calorie snack i.e. plain rice cakes is allowed till breakfast. Water and other fluids are to be restricted one hour before and one hour after dosing (excluding amount of water allowed for IMP administration.

9.12. Day 28

On Day 28, patient is to receive the last dose of IMP. Before administration (≤ 1h before IMP administration) vital signs measurements (respiratory rate, body temperature, 3-positional blood pressure and pulse) are to be performed, followed by 12-lead ECG. Afterwards blood and urine samples for clinical laboratory assessments, and blood sample for pre-dose PK time point (extensive and sparse group) are to be collected (\leq 1h before IMP administration). With the first blood sampling cannula might to be inserted into a vein shortly prior to the event. If there is cannula occlusion, samples may be obtained via direct venepuncture. IMP is to be administered with hand and mouth check afterwards to ensure the patient have swallowed all capsules. Within 5 minutes before or after 1h 45 minutes after IMP administration vital signs measurements are to be performed (respiratory rate, body temperature, 3-positional blood pressure and pulse). Start of ratings is to be within 5 minutes before or after 2h post-dose but after PK blood collection 2h timepoint (extensive and sparse group) and the scales are to be performed in order as follows: PANSS, CGI-S, CGI-I, BACS, ESRS, C-SSRS. Not earlier than 5h post-dose physical, neurological, ophthalmological and dermatological examination are to be performed. Within 5 minutes before or after 9h post-dose vital signs measurements are to be performed (respiratory rate, body temperature, 3-positional blood pressure and pulse).

Requests for AE and information about the concomitant medications if any, are to be performed by the Investigator to each patient during the study as well as subject is to be asked to report spontaneously all symptoms and complaints.

Patient is to fast from supper on day before (fasting at least 10 hours prior to dosing) with continued fasting for 2 hours post-dose. Water and other fluids are to be restricted one hour before and one hour after dosing (excluding amount of water allowed for IMP administration.

9.13. Day 29

Starting from Day 29 there are no IMP administration. On Day 29, the patient may resume antipsychotic treatment. Urine pregnancy test is to performed for women patients. Requests for AE and information about the concomitant medications, if any, are to be performed by the

Investigator to each patient during the study as well as subject is to be asked to report spontaneously all symptoms and complaints.

At the Investigator discretion patients will be discharged from the clinical unit based on local standards of care, if the patient is in a stable condition under the regular medication(s).

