1. PROTOCOL SUMMARY

1.1. Protocol Synopsis

Protocol Title	Phase II, Double-blind, Randomized, Placebo-controlled, Parallel-group, Trial to Explore Efficacy, Safety and Pharmacokinetics of CPL500036 (PDE10A inhibitor) in Patients with an Acute Exacerbation of Schizophrenia
Study Numbers	Sponsor Protocol No.: 02PDE2019
Development Phase	Phase II
Sponsor	Celon Pharma S.A.
Study Centers	This study will be conducted at multiple clinical units.
Study Objectives	Primary Objective:
	Efficacy:
	To determine if CPL500036 administered for 28 days can attenuate the positive symptoms associated with schizophrenia.
	Secondary Objectives:
	Efficacy:
	• To determine if CPL500036 administered for 28 days can attenuate the negative symptoms associated with schizophrenia.
	• To determine if CPL500036 administered for 28 days results in overall clinical improvement as assessed by the Clinical Global Impression Scale - Improvement (CGI-I).
	• To determine if CPL500036 administered for 28 days results in overall clinical improvement as assessed by the Positive and Negative Symptom Scale (PANSS).
	Safety:
	• To assess the safety and tolerability of CPL500036 administered for 28 days.
	Pharmacokinetics:
	To assess the pharmacokinetic (PK) profile of CPL500036 administered for 28 days.
Study Design	This is a double-blind, randomized, placebo controlled, parallel group, dose ranging study to explore the efficacy, safety, tolerability and PK of 2 different doses of CPL500036 (phosphodiesterase 10A [PDE10A] inhibitor) in patients with an acute exacerbation of schizophrenia when administered for 28 days.
	The study will be conducted at multiple clinical units. Approximately 165 patients will be randomized at a 1:1:1 ratio to receive 20 mg CPL500036, 40 mg CPL500036 or placebo.
	The study will comprise of a Screening Period (that will include a prior Medication Washout Period), a Treatment Period and a Follow-up Period.
	For the Screening Period, patients will undergo screening assessments from Day -10 to Day -8 in multiple settings (i.e., emergency departments, outpatient clinics, etc.). Rolling admission will be employed in this study. Patients that fulfil all the inclusion criteria and none of the exclusion criteria will immediately be admitted to the Clinical Unit and enter a Medication Washout Period of up to 7 days (Day -7 to Day -1) before the randomization on Day 0. The duration of the Medication Washout Period may be shorter or omitted for non-medicated patients.

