5.4. Restrictions

5.4.1. Dietary and Fluid Restrictions

Caffeine

Xanthine containing products (e.g., caffeine in coffee, tea, chocolate) will not be allowed from 24 hours prior to Day 1 to Day 28, inclusive. Subjects should not consume caffeine containing beverages exceeding 500 mg caffeine per day (5 cups of coffee) during the off-site days during the study.

Alcohol

Consumption of alcohol and alcohol-containing foods, medications or beverages must be avoided from 48 hours prior to Day -1 and while subjects are confined to the study center. Subjects should not consume more than 3 units (males) or 2 units (females) per day during the study Follow-up period (1 unit is equal to approximately ½ pint [284 mL] of beer, one small glass [125 mL] of wine, or one measure [25 mL] of spirits).

Meals

No outside food or drink is permitted at the study center. During in-house stay at the study center only meals and fluid intake according to the study center's meal plan will be allowed.

Fasting

Dosing Day: Dosing during treatment period will take place after an overnight fast of at least 10 hours. Water intake will be allowed up to 1 hour before dosing and from 1 hour after dosing (excluding amount of water allowed for IMP administration).

After IMP administration patients should remain fasting:

- On Day 1, Days 2-6, Day 7 and Day 28: up to 2 hours,
- On every other day: up to 2h but starting from 0.5h after IMP administration consumption of low calorie snack i.e. plain rice cakes is allowed till breakfast.

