6.4.2. Randomization Numbers

Prior to dosing, on Day 0, subjects will be assigned a randomization number in accordance with the randomization code generated by eCRF platform. Randomization procedure is to be performed to minimize bias in the assignment of subjects to treatment groups. Subjects are to be randomized in 1:1:1 ratio (a stratified block is to be implemented: geographical location, PK group, PANSS baseline score).

Once a randomization number has been allocated to one subject, it may not be assigned to another subject.

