6.5. Administration of Investigational Medicinal Products

Starting from Day 1, the IMP will be administered after a minimum 10-hours overnight fast with approximately 240 mL water. Subjects must remain in an upright position for at least 2 hours after dosing. The IMP is to be administered approximately at the same time each day.

Fasting requirement after IMP intake are described in Section 5.4.1.

For dosing details, see Section 6.6 below.

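### Section 9.4 starts the fast for the Day 1 dose at supper on Day -1, although Day 0 now lies between, which contradicts the overnight-fast rule elsewhere in the protocol

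*Protocol*

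**What the plan says.** The instruction for the first dosing day (Protocol Section 9.4) is "Patient is to fast from supper on Day -1 (fasting at least 10 hours prior to dosing"). The same section fixes the dosing day: "On Day 1, patient is to receive the first dose of IMP".

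The protocol's calendar puts a full study day between those two points. Table 1 gives Day 0 its own column. Section 6.4.2 states "Prior to dosing, on Day 0, subjects will be assigned a randomization number". Section 9.3 is devoted to it: "On Day 0, the Investigator is to performed the final patient qualification to the study based on all baseline results". The synopsis describes a "Medication Washout Period of up to 7 days (Day -7 to Day -1) before the randomization on Day 0".

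The general fasting rules are different. Section 5.4.1: "Dosing during treatment period will take place after an overnight fast of at least 10 hours". Section 6.5, which applies from Day 1 onward: "the IMP will be administered after a minimum 10-hours overnight fast". For the remaining dosing days, Sections 9.5 to 9.12 use a relative day: "Patient is to fast from supper on day before (fasting at least 10 hours prior to dosing").

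**The concern.** Section 9.4 is the only dosing-day section that names a numbered day for the start of the fast, and in the current calendar that day is not the eve of dosing. A site working from it as written would withhold food from supper on Day -1, through all of Day 0, until two hours after the Day 1 dose. The ten-hour figure in the same sentence does not prevent this, because it is a minimum and a longer fast also satisfies it.

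The Day 1 measurements at stake, at any site that reads the sentence literally, are:

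- **Safety baselines.** SAP Section 4.1.1 takes the Day 1 pre-dose vital signs and the Day 1 laboratory values as baseline. Blood pressure is measured in three positions, and Table 8 of the protocol includes glucose, triglycerides, uric acid and urinary ketones. A different fasting state at baseline would enter the change-from-baseline and shift tables of SAP Sections 4.8.2 and 4.8.3.1.
- **Day 1 PK.** The Day 1 profile is the single-dose reference. SAP Section 4.10 forms accumulation ratios as Day 7 over Day 1.
- **Day 1 PANSS.** It is one of the time points in the primary repeated-measures model (SAP Section 4.7.1).

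If sites resolve the conflict differently, Day 1 conditions also vary between sites. Protocol Section 11.7 asks for exact adherence, and Section 7.1.1.1 lists breaches of dietary rules that may affect results among the grounds for withdrawal, so staff need one unambiguous instruction.

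**Working it through.** **Inputs from the documents**

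| Item | Value | Source |
|---|---|---|
| Fast for the first dose begins | supper, Day -1 | Protocol 9.4 |
| First dose | Day 1 | Protocol 9.4 |
| Day between them | Day 0 | Table 1, 6.4.2, 9.3 |
| General rule | overnight, at least 10 h | Protocol 5.4.1, 6.5 |
| Fast for other doses begins | supper, preceding day | Protocol 9.5–9.12 |

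**Inputs assumed.** Neither document gives a supper or dosing time. I take supper at S = 17:00–19:00 and dosing at D = 07:00–09:00, then widen both.

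**Formula.** With k whole calendar days between the supper day and the dosing day,

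fast (h) = (24 − S) + 24k + D.

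**Step 1: the plan's own rule.** Supper on the preceding day means k = 0.

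- Shortest: (24 − 19) + 0 + 7 = 12 h
- Longest: (24 − 17) + 0 + 9 = 16 h

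The result, 12–16 h, is an overnight fast above the ten-hour minimum, so Sections 5.4.1, 6.5 and 9.5–9.12 agree with one another.

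**Step 2: Section 9.4 as written.** Supper on Day -1 with Day 0 between means k = 1.

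- Shortest: (24 − 19) + 24 + 7 = 36 h
- Longest: (24 − 17) + 24 + 9 = 40 h

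Adding the two-hour post-dose fast gives 38–42 h.

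**Step 3: sensitivity.** With supper at 17:00–22:00 and dosing at 07:00–10:00:

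- k = 0: from (24 − 22) + 7 = 9 h to (24 − 17) + 10 = 17 h
- k = 1: from 9 + 24 = 33 h to 17 + 24 = 41 h

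The 9 h corner would itself fail the ten-hour minimum.

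**Step 4: what does not depend on the assumptions.** The difference between the two readings is 24 × (1 − 0) = 24 h for any S and D. A fast of 33 h or more meets the ten-hour minimum but spans a whole day, so it does not fit the overnight requirement.

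**The case against.** The strongest reply is that the intent is recoverable. Section 6.5 applies the overnight rule expressly from Day 1. The disputed sentence carries the same ten-hour parenthesis as the other dosing days. Section 9.3 places no food restriction on Day 0, and Section 5.4.1 has inpatients eating to the centre's meal plan. The amendment log shows that Day 0 was introduced with protocol version 3.1 (July 2021) and lists no edit to the Day 1 fasting sentence, which suggests a day label left behind. Other text also runs without a Day 0: Protocol Sections 8.7 and 9.1 go from washout to treatment, and the relative-day formula in SAP Section 4.1.1.1 numbers the calendar day before the first dose as −1. Most of this stands, and many sites may have used an overnight fast. It does not remove the conflict. The SAP's numbering is an analysis convention, not a site instruction. Section 9.3 could hint that Day 0 is needed only when results are late, but Section 6.4.2 and Table 1 place randomisation there unconditionally.

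Three stronger readings might be inferred, and the documents do not support them:

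- **That all of the approximately 165 patients had a prolonged fast.** This needs every site to follow 9.4 against 5.4.1 and 6.5, and every patient to have enrolled after Day 0 was added. Neither is documented.
- **That the PK accumulation results are confounded.** Day 1 and Day 7 are fasted under either reading, and nothing in the documents shows that a fast longer than overnight changes exposure. The accumulation ratios are exploratory, and Day 28 has only pre-dose and two-hour samples, so there is no full profile to compare.
- **That the efficacy comparison is biased.** The fasting instruction is the same in all three arms, the PANSS baseline is the Day -1 rating, the primary endpoint is at Week 4, and clinical site is a fixed effect in the model.

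**Conclusion.** The contradiction is real and lies in the current text. Section 9.4 cannot be followed as written together with the overnight rule in Sections 5.4.1 and 6.5, given the Day 0 calendar, and it departs from the pattern of Sections 9.5–9.12.

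The size that rests on the documents alone is 24 extra hours of fasting before the first dose under a literal reading. The figures of 36–40 h against 12–16 h are illustrations that depend on the assumed meal and dosing times.

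The consequences are conditional. They arise only at sites that applied 9.4 literally, and they concern the Day 1 vital-sign and laboratory baselines, the Day 1 PANSS and the Day 1 PK profile. How many patients that covers is unknown, and no change in drug exposure is shown. Because this is an operative instruction to sites on acutely ill inpatients, it should be corrected, but it does not call the primary analysis into question.

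**What to change.** Reconcile Section 9.4 with Sections 5.4.1, 6.5 and 9.5–9.12 and with the calendar that contains Day 0, so that the day on which the fast for the first dose begins is stated once and consistently. Tell sites which text governs. Which rule applies is for the sponsor to decide. If patients have already been dosed under a schedule with Day 0, ask each site how it applied the sentence, so that the Day 1 baselines and PK can be read accordingly.

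The cost is a few words in the protocol and a clarification to sites. No analysis has to change.
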